Anemic patients scheduled to undergo CABG, valve, or CABG/valve surgeries will be considered for the study. Patients who fulfill all the inclusion/exclusion criteria will be asked to participate in the study. The proportion of screen failures and eligible patients who refuse to participate will be recorded using a screen failure log. Patients who agree to be in the study and sign an informed consent form will be sequentially enrolled into the treatment group. The treatment group will receive up to three doses of EPO 300U/kg. The first dose of study medication will be administered up to 28 days before the day of surgery and the second will be administered 1-7 days before the day of surgery. These first two doses will be given at least 7 days apart. A third dose may be administered two to four days following surgery. All 3 doses will be administered subcutaneously and per surveillance strategy guidelines. In addition, supplementation

with IV iron (feraheme; 510mg delivered per IV infusion over a minimum of 15 minutes) will be given following the first two preoperative doses of EPO.

Differences in hemoglobin levels and reticulocyte counts from baseline to the day of surgery (preop to POD#0) and postoperative day five (POD#5), proportion of patients receiving erythrocyte transfusions and number of blood products (RBC, platelets and plasma) utilized and pre-defined clinical events (mortality, major cardiac, renal, neurological events [associated with anemia] and infection) will be assessed in all treated participants. Each patient will be enrolled in the study up to 28 days before the day of surgery and for up to 30 days following the day of surgery. This feasibility propensity-matched study will sequentially enroll 23 more treatment subjects to total 25. The propensity-matching control group will be comprised of 25 total “like” patients for comparison. The source of the data for the control group will be the Society of Thoracic Surgery (STS) Database, an institutional registry.

Study medications:

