The decision to initiate and continue administering doses of EPO is based on evidence accrued from randomized controlled trials and clinical practice guidelines provided by multiple sub-specialty and international societies.^{14,40-41} Substantial heterogeneity exists in factors that could be included in a surveillance strategy to minimize the risk of a thrombotic event in this setting; with no one strategy proven to be superior. The surveillance strategy included in this protocol derives from, what we believe to be, the most current safety analyses of perioperative EPO use reflected in the literature. Implementing such surveillance methods are intended to minimize the possibly rare but potentially life-threatening adverse events. Risk factors considered in our surveillance strategy include: evidence of unstable angina or myocardial infarction, recent thrombotic event, hemoglobin levels associated with a higher risk of a

myocardial event, excessive thrombocytosis (platelet count $>300 \times 10^3/\mu\text{L}$) or laboratory evidence of a hypercoagulable postoperative state.

EPO dosing will be stratified based on patient risk (degree of perioperative anemia), type of procedure (CABG vs. valve) and laboratory data (Hb, RoTEM: MCF) in the following manner:

Initial dosing/Re-dosing of EPO plus IV iron (Prior to Surgical Procedure):

Therapy or a dose will **NOT** be administered in patients under the following conditions:

- Patients scheduled for a CABG procedure with Hb concentration $\geq 12.5\text{g/dL}$
- Patients scheduled for a cardiac valve procedure with Hb concentrations $\geq 13.5\text{g/dL}$
- Rate of rise in Hb level that exceeds 1g/dL in past 7 days (and not secondary to erythrocyte transfusion)^a
- Evidence of any new or evolving symptoms or signs suggesting the presence of myocardial ischemia, including chest pain, EKG changes, or elevation of laboratory cardiac biochemical (CK-MB, Troponin)
- Average of three diastolic blood pressures (over 1hr) $>100\text{mmHg}$ despite scheduled anti-hypertensive therapy.

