^a **Rationale:** The original label for EPO²⁹⁻³⁰ included a warning regarding the risk of exacerbation of hypertension with hematocrit increases exceeding 4 percentage points (corresponding to increases in the hemoglobin concentration of approximately 1.3 g per deciliter) within a 2-week period. During a review of the marketing application, an association was found between rates of increase in the hemoglobin level exceeding 1g/dL per 2-week period and the risk of cardiovascular and thromboembolic events. This observation provided the basis for a warning on the package insert for darbepoetin regarding excessive rates of increase in hemoglobin concentrations.

Continuation of Dosing of EPO (Post-Operative Administration)

Postoperative therapy will **NOT** be administered in patients under the following conditions:

- Hb concentration $>10.0\text{g/dL}$ (both CABG and valve procedures)^b
- Rotational Thromboelastogram (RoTEM) measurement of Maximum Clot Firmness (MCF) $>70\text{mm}$ (RoTEM to be performed during procedure and 2-4 days after surgery, prior to re-dosing).
- Evidence of any new or evolving symptoms or signs suggesting the presence of myocardial ischemia, including chest pain, EKG changes, or elevation of laboratory cardiac biomarkers (CK-MB, Troponin) that have failed to have a decreasing trend
- Average of three diastolic blood pressures (over 1hr) $>100\text{mmHg}$ despite scheduled anti-hypertensive therapy.

^b **Rationale:** A multi-center study in over 2,000 CABG patients by Spiess et al.¹² demonstrated that hematocrit $>34\%$ (11.3g/dL) upon entry in the ICU was the single greatest predictor of myocardial infarction following surgery. Furthermore, according to the labeling for EPO targeting higher hemoglobin (13 to 14g/dL) compared to a lower range (9 to 11.3g/dL) increased the risk of death, myocardial infarction, stroke, and thrombotic events in patients *with CKD*.²⁹⁻³⁰

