1. The subject must be between the age of 18 and 80 years old.
2. The subject must be diagnosed with preoperative anemia, defined as hemoglobin <13.0g/dL.
3. The subject must be scheduled for elective cardiac surgery (CABG, valve, or CABG/valve), including both first time and repeat procedures.
4. Female subjects of child bearing potential must have a documented negative pregnancy test within 7 days prior to the procedure.

5. The subject must sign a written informed consent prior to the procedure, using a form that is approved by the UT Southwestern Institutional Review Board.
6. The subject must agree to be compliant and return for all follow-up visits.

VII. CRITERIA FOR EXCLUSION OF SUBJECTS:

The subjects will be excluded if they meet any one of the following criteria:

1. Uncontrolled hypertension (defined as systolic pressure greater than 180mmHg, diastolic pressure greater than 100mmHg, not adequately controlled by anti-hypertensive therapy at the time of procedure).
2. Current renal failure on dialysis or serum creatinine [Cr]>3.0mg/dL. ¹
3. Unstable angina (defined by chest pain and ECG changes indicating ischemia at rest).
4. Thromboembolism within the past year.
5. Current active primary or metastatic malignancy or history of myeloid malignancy.
6. Seizures within the past year.
7. History of stroke within the last 6 months.
8. Patients who have platelet count lower than 50,000/mm³ or coagulation abnormality.
9. Sepsis or bacteremia defined by positive blood culture.
10. Patients who have known hypersensitivity to EPO or any of its components.
11. Patients who have known hypersensitivity to Feraheme or any of its components.
12. Patients who refuse blood transfusion, (i.e. Jehovah's Witnesses).
13. Pregnant or breast feeding.
14. Patients who are unable to provide informed consent or who has inability to understand or cooperate with study procedure.

VIII. SOURCES OF RESEARCH MATERIAL

Data will be obtained from the patient's medical records EPIC and the Society of Thoracic Surgery (STS) database entries. Laboratory tests for reticulocyte count and additional serum ferritin, cardiac biomarkers, serum creatinine, thromboelastographic and liver transaminase measurements will be obtained specifically for research purposes. Other tests conducted (e.g. hemoglobin concentration, creatinine, EKG) will be part of standard of care (see Table 1 for details regarding standard of care and for research only).

IX. RECRUITMENT METHODS AND CONSENTING PROCESS

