Because clinical trials have been conducted under widely varying conditions, adverse reaction rates observed in clinical trials of EPO may not reflect rates observed in our study. The black-box warning issued by the FDA for *chronic* use of erythrocyte stimulating agents in patients with end stage renal disease (ESRD) *and* cardiovascular disease (for increased risk of thrombotic and cardiovascular events) has been challenged by more recent publications outlining differences in the safety profile for short-term use in the perioperative setting. It is important to understand the differences in our patient population when comparing the adverse events listed on the package insert for this drug. First, the majority of adverse events reported by EPO clinical trials have been in chronic renal failure patients and in cancer patients receiving chemotherapy, whom we exclude from our study. Second, our protocol is a short-term (1-4 weeks) in patients experiencing moderate-to-high levels of acute hemorrhage (750mLs-1,500mLs). Third, all of the patients in our study will be anemic; thus the likelihood of having a hematocrit at a level likely to result in a thrombotic complications following CABG surgery is unlikely. Erythrocyte stimulating agents have been used in clinical practice at our institution for over 2 years and increases in the rates of seizure, thrombotic events, pure red blood cell dysplasia, or serious allergic reactions have *not* been observed in patients receiving these medications. The only side effect that has been observed is hypertension. In our study, treatment will be held in patients with blood pressure above 180/100mmHg.

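### If *the procedure* in inclusion criterion 4 means the operation, no pregnancy test is required before the first dose of EPO and iron, except when that dose falls on day −7

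*Combined protocol and SAP*

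**What the plan says.** All references are to the combined protocol and SAP.

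- **Test.** Section VI, item 4: "Female subjects of child bearing potential must have a documented negative pregnancy test within 7 days prior to the procedure". No other pregnancy test is named in the text supplied.
- **First dose.** Under Baseline Research Visit (section III), EPO 300 U/kg and iron 510 mg are given 7 to 28 days before surgery. Section IX gives the same range when the first dose is booked as a separate appointment.
- **Second dose.** Research Design and Methods (section III) places it 1 to 7 days before surgery and at least 7 days after the first.
- **Eligibility.** The same part of section III says "Patients who fulfill all the inclusion/exclusion criteria will be asked to participate in the study". Table 1 marks the eligibility check once, in the 7-28d PreOp column.
- **Pregnancy exclusion.** Section VII, item 13 rules out pregnant and breast-feeding patients without asking for a test. The baseline visit reviews laboratory results already on file. Table 1 has no pregnancy-test row, and the research laboratory list in section VIII does not name one.
- **The word *procedure*.** It is undefined. Section VI, item 3 uses it for operations ("including both first time and repeat procedures"). So does the Surveillance Strategy in section III: "Patients scheduled for a CABG procedure with Hb concentration" and "RoTEM to be performed during procedure and 2-4 days after surgery". Other uses are looser. Section VI, item 5 says "The subject must sign a written informed consent prior to the procedure". Section VII, item 1 describes blood pressure "not adequately controlled by anti-hypertensive therapy at the time of procedure", while section X applies the same limit to dosing: "treatment will be held in patients with blood pressure above 180/100mmHg".

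**The concern.** A pregnancy test at entry to a drug study would normally come before exposure. Here the drugs start up to four weeks before the operation. A test timed from the operation therefore falls after the first dose for nearly all permitted schedules.

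What is at stake is exposure of an unrecognised pregnancy to EPO and iron before any test that the protocol requires. A second, practical problem is that a sensible test done just before a first dose on day −28 to −8 would be too early to satisfy the criterion. This is a matter of participant safety and eligibility timing. It does not touch the statistical analysis.

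**Working it through.** The plan gives no figure to reproduce, so the check is a comparison of day windows. Day 0 is the day of surgery, and *the procedure* is taken to mean the operation.

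**Inputs**

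| Item | Days | Source |
|---|---|---|
| Qualifying test | −7 to 0 | Section VI, item 4 |
| First dose | −28 to −7 | Section III, Baseline Research Visit; section IX |
| Second preoperative dose | −7 to −1 | Section III, Research Design and Methods |
| Gap between these doses | at least 7 days | Section III, Research Design and Methods |

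**1. Permitted first-dose days.** 28 − 7 + 1 = 22.

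**2. Overlap with the test window.** {−28, …, −7} and {−7, …, 0} share only day −7. That is 1 of 22 days. On the other 22 − 1 = 21 days (−28 to −8) the test window has not opened. Day −7 itself works only if the test is done before the dose that day.

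**3. Delay from first dose to the earliest qualifying test.** For a first dose on day −d the delay is d − 7 days. For d = 8 it is 1 day; for d = 28 it is 21 days. The range is 1 to 21 days.

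**4. Patients given two preoperative doses.** The latest second dose is day −1, so the first must be on day −1 − 7 = −8 or earlier. Days −28 to −8 do not meet the test window at all. A test on day 0 would also satisfy the criterion, and it would come after the second dose as well.

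**5. Timing the test from the first dose instead.** A test within 7 days before the first dose falls on day −35 to −28 for a dose on day −28, day −21 to −14 for a dose on day −14, and day −14 to −7 for a dose on day −7. A negative result then precedes exposure on all 22 days.

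**6. Why the pre-surgery test should stay.** If the first-dose test replaced it, a test on day −35 would be 35 − 1 = 34 days old at a second dose on day −1, and 35 days old at surgery.

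**7. When one test can serve both purposes.** It must fall no later than the first dose (day −7 at the latest) and no earlier than day −7. That leaves only a test on day −7 with the first dose the same day. All other schedules need two tests.

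**Other reading.** If *the procedure* means the first study treatment, the test already precedes exposure and every gap above disappears.

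**The case against.** The strongest objection is that the premise is unsettled. Items 4 and 5 of section VI share the same closing phrase. Item 5 concerns consent, which has to come before the first dose, so it does its job as an entry rule only if the phrase means study treatment. Section VII, item 14 and the title of section IV also attach the word to the study rather than to the operation. This stands, and it is why the point is conditional. It does not remove the need for clearer wording, because item 3 and the Surveillance Strategy use the word for the operation and dosing is elsewhere called dosing or therapy.

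Three stronger readings are tempting, and the documents do not support them.

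- **A reader might infer that these women can enter only on day −7 and so lose a preoperative dose.** That treats the invitation rule as a strict gate. But signed consent is itself an inclusion criterion and cannot be met before a patient is asked. The screening text in section III also speaks of initial entry criteria, which suggests staged checking. Table 1's single early check points the other way, so the matter is open.
- **A reader might infer that the criterion serves no safety purpose.** The protocol states no purpose for it. On the operation reading it still secures a recent negative test before surgery, and hence before any postoperative dose. Exclusion 13 also keeps out known pregnancies.
- **A reader might infer that no test is done at entry.** Table 1 is not a full list of eligibility tests: it has no row for blood cultures or coagulation studies either, although section VII relies on both. The timeline and flow figures and the consent pages were not available. The text does not require a test before dosing; it does not show that none is done.

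It is also fair to say that 1 of 22 counts calendar days, not patients.

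**Conclusion.** The point holds as a minor, conditional one. On the likelier reading, criterion 4 times the test from the wrong event for the first dose. The windows meet on 1 of 22 permitted days, and on none for a patient who gets two properly spaced preoperative doses. Otherwise EPO and iron can precede the earliest qualifying test by 1 to 21 days. The gap is limited to unrecognised pregnancy.

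This rests on reading *the procedure* as the operation, in which confidence is medium. On the first-dose reading the effect is zero and only the wording needs attention. The documents do not give the number of women of child-bearing potential. Among 25 treated cardiac surgery patients, 23 of them still to be enrolled, few are likely and there may be none; that is an assumption. No endpoint, estimate or analysis changes.

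**What to change.** Reword section VI, item 4 so that women of child-bearing potential need a documented negative pregnancy test within 7 days before the first dose of study drug. Keep a test within 7 days before surgery as a separate requirement, and allow one test to serve both if it falls in both windows. Add both tests to Table 1 for these patients: one in the 7-28d PreOp column and one before surgery.

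The cost is amendment wording, the Table 1 entries and, for a few patients, one additional inexpensive test. If the investigators already mean the first dose, the reworded criterion makes that explicit, and the test before surgery becomes the additional one.

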surveillance strategies. We define successful adherence as adhering to dosing in $\geq 90\%$ of patients for $\geq 90\%$ of the doses deemed appropriate by the surveillance strategy. Secondary outcomes will include:

- 1) changes in hemoglobin levels and reticulocyte counts within the two groups from baseline to the day of surgery (preop to POD#0) and POD#5;
- 2) proportion of patients receiving erythrocyte transfusions and number of blood products (RBC, platelets and plasma) utilized;
- 3) incidence of pre-defined clinical events (mortality, major cardiac, renal, neurological events [associated with anemia] and infection) in each of the study groups.

[figure not shown]
These events will include myocardial infarction, prolonged low-output state, stroke, encephalopathy, duration of mechanical ventilation, renal insufficiency, and mortality and dialysis dependence at 30 days or discharge. Data from this feasibility study will be used for the power analysis and design of the larger RCT.

Clinical events will be defined using the following criteria: Society of Thoracic Surgery (STS)⁴² for stroke/transient ischemic attack (TIA), coma/encephalopathy, myocardial infarction (MI), prolonged ventilation, reoperation for bleeding or graft occlusion/revision, postoperative venous thrombosis, thromboembolic event, deep venous thrombosis and pulmonary embolism; RIFLE⁴³⁻⁴⁴ for acute renal injury (AKI), National Healthcare Safety Network (NHSN)⁴⁵ for surgical site infections (SSI); Surgenor SD et al.⁴⁶ for low output heart failure (LOHF); any life-threatening events (i.e., subject was at substantial risk of dying at the time of the adverse event) and in-hospital or 30-day mortality based on observation. Outcome data will be collected via contact with primary physician, public record review or by a follow-up telephone call by the research nurse.

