The cost of erythrocyte transfusions, EPO plus iron, direct hospital costs and direct margins associated with the care of those randomized in this pilot study will be recorded for future analysis of resource utilization. The duration of operating room time, intensive care unit and hospital length of stay will be collected. The total cost of erythrocyte transfusion will be based on four times the acquisition cost (\$1,200.00)⁴⁷ The cost of EPO and IV iron will be calculated based on recommended manufacturer suggested retail price at the time of publication and will include activity based costs of administering these treatments based on the protocol outlined in this study.

IV. STUDY PROCEDURES:

Time Line of Pilot Study

Note: Supplementation with intravenous iron (feraheme; 510mg delivered as an IV infusion) will only be administered following the first two preoperative doses of EPO (shown in diagram).

Consort Diagram of Pilot Study:

[figure not shown]

Table 1. SUBJECT SCHEDULE OF EVENTS

Test/evaluation & collected/required forms	7-28d PreOp	1-7d PreOp	POD0 PreOp	POD0 PostOp	POD 1	POD 2	POD 5	POD 7	POD 14
Inclusion & exclusion criteria	X								
Informed consent/HIPAA	X								
Demographics	X								
Medical History/Meds	X								
Physical examination	X	X	X	X	X	X	X	X	X
Body mass index	X								
Vital signs	X	X	X	X	X	X	X	X	X
ASA	X								
Laboratory									
CBC	S	S	S	S	S	S	S	S	S/X
Reticulocyte Count	S	X		X	S		X	X	
Iron panel**	S		X		S		X		
Creatinine	S	S	S	S	S	S	S	S	S/X
Troponin T/CK-MB		X		S	S	S/X			
AST/ALT		S			S		X		
Rotational Thromboelastogram (Rotem) ⁺				S		X			
12-lead EKG	S	S	S	S	S	S	S	S	
Record of Erythrocyte transfusion	X	X	X	X	X	X	X	X	X
Estimated blood loss				X	X	X			
Adverse Events	X	X	X	X	X	X	X	X	X
Patient Survey	X								
Protocol Compliance	X	X	X	X	X	X	X	X	X

S = Standard of Care laboratory tests routinely ordered per ICU care team

X = Not routinely ordered laboratory tests; obtained for research purpose only.

*Will obtain hemoglobin and creatinine on POD14 or before hospital discharge (whichever event occurs first)

**Iron panel includes ferritin, TIBC, iron, transferrin

⁺ Will obtain RoTEM EXTEM 2-4 days after surgery

Adverse events and survival will be reviewed at the time of hospital discharge and 30d following surgery.

V. SUBSTUDY PROCEDURES

Our study does not include any sub-studies.

VI. CRITERIA FOR INCLUSION OF SUBJECTS:

The inclusion criteria of subjects are as follows:

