Adverse events are events that involve physiological, social, or psychological harm to subjects or risks of harm to additional subjects or others. AEs include expected and unexpected harmful effects, and unexpected risks of an interaction or an intervention. AEs may be caused by: the test article or test procedure, other aspects of the interaction or intervention, the subject's underlying condition, or the subject's concurrent standard treatment. AEs may be definitely related, probably related, possibly related, unlikely to be related, or definitely not related *to the research*.

B. Method of Identifying, Recording, Monitoring and Reporting Adverse Events:

We will report all adverse events and other reportable incidences and occurrences to the IRB per reporting guidelines. Any adverse event will be documented of that event including a description, subject number, date, outcome, and follow-up.

C. Safety Endpoints:

The primary safety endpoints of the study are the incidence of adverse events associated with the use of the study medications. These include: hypersensitivity (e.g. pruritis, rash, and urticaria), hypertension, hypotension, bleeding, nausea, vomiting, injection site pain, deep venous thrombosis or other thrombotic complications. Surveillance for these adverse events will be conducted by direct observation (during drug administration), daily bedside visits by the research nurse for the first 7 postoperative days, review of the patient's medical record and listing any of these complication in the Society of Thoracic Surgery (STS) database. The definition of a stroke, myocardial infarction (MI), mesenteric artery occlusion or peripheral vascular event will be based on STS criteria.³⁷ Any event resulting in death from time of initial drug administration to hospital discharge will be recorded.

XII. PROCEDURES TO MAINTAIN CONFIDENTIALITY

We will collect data from lab tests and EPIC, the electronic medical record.

Raw data: We will remove personal identifying information of the patients from the raw data and replace them with coded IDs before data processing and analysis. Any materials containing personal identifying information will be stored in a locked cabinet in the principal investigator's office. After data entry, any materials containing personal identifying information will be promptly and securely returned to the principal investigator. Any materials with personal identifying information on them will be shredded before discard.

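### Nothing in the supplied plan requires new dosing to pause for review if deaths or thrombotic events accumulate among the 25 treated patients; a fixed pause rule would be a cheap safety improvement

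*Combined protocol and SAP*

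**What the plan says.** Section XI.B sets the study-level process: "We will report all adverse events and other reportable incidences and occurrences to the IRB per reporting guidelines". Each event is also to be documented with its description, date, outcome and follow-up. Section XI.C lists the safety endpoints, thrombotic complications among them. It describes surveillance by observation during dosing, daily research-nurse visits for the first 7 postoperative days, record review and the STS database. The Table 1 footnote adds: "Adverse events and survival will be reviewed at the time of hospital discharge and 30d following surgery". Clinical Outcomes relies on STS definitions for MI, stroke and "postoperative venous thrombosis, thromboembolic event, deep venous thrombosis and pulmonary embolism", and captures "in-hospital or 30-day mortality based on observation".

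The rules that withhold a dose are in Surveillance Strategy for ESA Dosing and in Section X. Each depends on that patient's own hemoglobin, rate of hemoglobin rise, signs of ischemia, blood pressure or postoperative clot firmness. Their purpose is stated: "Implementing such surveillance methods are intended to minimize the possibly rare but potentially life-threatening adverse events". Section VII excludes, among others, patients with unstable angina, thromboembolism in the past year or stroke in the past 6 months.

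On scale, Section III says: "This feasibility propensity-matched study will sequentially enroll 23 more treatment subjects to total 25". Each patient is in the study "up to 28 days before the day of surgery and for up to 30 days following the day of surgery". On the comparison group: "The source of the data for the control group will be the Society of Thoracic Surgery (STS) Database, an institutional registry". The Biostatistics section contains no interim safety look and no safety boundary.

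**The concern.** The plan gives its own reasons for caution. Section X says the use is off-label because safety and efficacy data in cardiovascular surgery are insufficient, and that EPO may raise the risk of cardiovascular events, including fatal ones. The Background says the earlier cardiac-surgery trials (810 subjects) were too small to settle safety. Treatment is lengthened from under 5 days to 1-4 weeks, and testing safety is a stated purpose.

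The dose holds respond to the patient in front of the clinician, not to what has happened to other patients. If two or three treated patients had a thrombosis or died, the text says the events are reported. It does not say whether the next patient may be dosed before anyone has looked at the cases. A threshold is also hard to set credibly once events are known, and 23 of the 25 treated patients are still to be enrolled. What is at stake is whether review of a cluster before further dosing is assured or depends on judgment at the time.

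**Working it through.** **Step 1: what triggers a stop, by section.**

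| Provision | Where | Trigger |
|---|---|---|
| Preoperative hold | Surveillance Strategy | that patient's Hb, Hb rise, ischemia, diastolic pressure |
| Postoperative hold | Surveillance Strategy | that patient's Hb, clot firmness, ischemia, diastolic pressure |
| Blood-pressure hold (180/100 mmHg) | Section X | that patient's pressure |
| Event documentation and IRB reporting | XI.B | each event; no count, no pause |
| Review at discharge and 30 days | Table 1 footnote | calendar time; no action stated |
| Statistical analysis | Biostatistics | no safety boundary |

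No row responds to the number of events across patients. The plan states no safety boundary, so there is no figure of its own to reproduce.

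**Step 2: inputs.** From the documents: 25 treated patients, 25 - 23 = 2 already enrolled, and a longest window of 28 + 30 = 58 days. The documents give no background rate for a composite of death, MI, stroke and thrombosis, and no accrual rate. The reference rate, true rates and lags below are therefore assumptions. The one adverse rate cited for EPO in cardiac surgery is 6% against 0% (Section X), from an aggressive regimen in mostly non-anemic patients.

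**Step 3: boundary.** Order patients by first dose. For the first n patients, b(n) is the smallest k of at least 2 with P(X >= k | n, p0) <= 0.05, X binomial. With p0 = 5%:

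- n = 7, k = 2: 1 - 0.95^7 - 7 x 0.05 x 0.95^6 = 1 - 0.698 - 0.257 = 0.044, so 2 suffices.
- n = 8, k = 2: 0.057, so 3 are needed.
- n = 16, k = 3: 0.043. n = 17, k = 3: 0.0503, so 4 are needed.
- n = 25, k = 4: 0.034.

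Boundary: 2 events for n = 2-7, 3 for n = 8-16, 4 for n = 17-25.

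**Step 4: chance of crossing.** Exact recursion over 25 patients, f_n(k) = f_{n-1}(k)(1 - p) + f_{n-1}(k - 1)p, with paths removed when k reaches b(n):

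| True rate | 5% reference | 10% reference |
|---|---|---|
| 5% | 0.08 | 0.01 |
| 6% | 0.12 | 0.02 |
| 10% | 0.33 | 0.10 |
| 15% | 0.61 | 0.28 |
| 20% | 0.82 | 0.51 |
| 30% | 0.98 | 0.86 |

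**Step 5: lag.** Let L be the further patients dosed before a crossing is recognized. Over 58 days (1.91 months), L = 4, 8 and 12 correspond to about 2.1, 4.2 and 6.3 patients a month. The crossing spares someone only if it occurs at patient n with n + L < 25. At a true 20% with a 5% reference:

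| Lag L | P(recognized with a patient undosed) | Mean treated | Mean left undosed | x (0.20 - 0.05) |
|---|---|---|---|---|
| 0 | 0.80 | 12.9 | 12.1 | 1.8 |
| 4 | 0.72 | 16.0 | 9.0 | 1.4 |
| 8 | 0.69 | 18.8 | 6.2 | 0.9 |
| 12 | 0.53 | 21.3 | 3.7 | 0.6 |

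The last column is excess events averted if background risk is 5%. At lag 8, events among dosed patients fall from 25 x 0.20 = 5.0 to 18.8 x 0.20 = 3.8, a drop of 1.2. Undosed patients still have surgery at background risk, so the excess averted is 6.2 x 0.15 = 0.9. These figures assume dosing never resumes after review, so they are best case.

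At a true 6%, mean treated is 23.3 to 24.5 across the same lags, so almost nobody is spared.

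**Step 6: anaphylaxis.** At the 3/1,726 quoted for serious hypersensitivity in Section X, 1 - (1 - 3/1726)^25 = 0.043. A single case would be unusual enough to review individually, outside the count.

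**The case against.** The strongest reply is that this is a preference. The study is small, open and apparently single-site. Every enrolled patient is known to be treated, and staff see each death or thrombosis as it happens. High-risk patients are excluded, doses are held on several criteria, and all adverse events go to the IRB. The documents also point to modest risk: no adverse-event difference in 810 subjects (though underpowered), no negative signal in later trials of anemic patients, and over 2 years of institutional use without an observed rise in thrombotic events. The plan itself calls the target events possibly rare. At 6% the proposed rule does almost nothing; its useful range is assumed.

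Most of that stands, and it is why the point is an improvement and not a defect. It does not remove the gap: seeing and reporting events differs from a commitment to pause.

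A reader might infer that patients are unmonitored, or that a cluster would go unreviewed. The documents do not support either. Surveillance is substantial, and the IRB guidelines, which are not in the supplied text, may require prompt review of deaths or unexpected events. The plan never says that a pause is discretionary; it is silent.

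Two technical objections also stand. The reference rate is unknown, and one set too low causes needless pauses. The outcomes of the two patients already enrolled may be known when the boundary is set, so they need disclosure.

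**Conclusion.** The point holds as a cheap safety improvement. The supplied text commits nobody to pause new dosing as events accumulate among the 25 treated patients.

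The benefit is confined to clearly raised rates. With a 5% reference, a true 20% crosses the boundary with probability about 0.82, but is recognized in time to spare at least one patient with probability 0.80, 0.72, 0.69 or 0.53 for lags of 0, 4, 8 or 12 patients. At lag 8 and 5% background, about 0.9 excess events are averted at best, and fewer if dosing resumes.

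It would be tempting to read a crossing as evidence that EPO caused the events. Without a concurrent randomized control it is not; it triggers review only. All rates and lags are assumptions, and the calculation takes patients as independent and in order of first dose.

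**What to change.** Add one paragraph and a small table to Section XI.B:

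- The principal investigator keeps a running count of treated patients with death, MI, stroke, DVT/PE or other thrombosis, from first dose to 30 days after surgery, using the STS definitions already adopted where they exist.
- New dosing pauses for IRB review when, for any n, the count among the first n dosed patients reaches the boundary.
- One rule is used: exact binomial tail at most 0.05, with at least 2 events. The reference is the site's STS registry rate for anemic CABG/valve patients, fixed before further enrolment. Note that events between first dose and surgery may have no registry counterpart. If the reference were 5%, the boundary in Step 3 would apply.
- The outcome status of the two patients already enrolled is disclosed when the boundary is set.
- Any anaphylaxis is reviewed case by case.
- Crossing probabilities are printed over a range of true rates and lags.

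The cost is an amendment and one registry query. The events are already collected and no committee is needed. The downside is an unneeded pause in about 8% of trials (5% reference) to 10% (10% reference) when the reference is right. This rises to about 33% if the reference is set at 5% and background is 10%, which is why the registry should supply it.
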